8.2 Protocol Deviations

Since this is a registry study, protocol deviations/violations will not be recorded.

8.3 Analysis Populations

8.3.1 Intent To Treat (ITT) Population

All patients where a cryoprocedure was attempted with a Galil Medical Cryoablation System and needles and who met the study eligibility criteria will form the Intent-to-Treat (ITT) population. This population will be used for the analysis of all efficacy and safety data. Patients in the ITT population will be identified as follows:

- 1) First include all patients with a date of cryotherapy recorded
- 2) Then exclude any patients who have been manually identified as having not met all eligibility criteria from a review of monitoring reports.

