8.3. Analysis Populations

All subjects completing a cryoablation procedure for removal of a renal lesion will be included in the analyses of TRACE data.

The full details of the approach to analysis of the data will be detailed in the Statistical Analysis Plan.

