10.1. Monitoring and Auditing

Participating TRACE sites will be managed remotely via regular telephone contact and, as necessary, on-site monitoring visits; no routine monitoring visits will be conducted. When necessary, site visits will be performed by an authorized representative from Galil and will be conducted according to applicable GCP and local regulatory guidelines.

In addition, sites may be subject to an audit visit by Galil or a local regulatory authority (e.g., FDA). If such a site audit occurs, the investigator agrees to provide access to all pertinent subject records, eCRFs and other site documents deemed necessary to complete the audit visit.

By signing the Registry Agreement, the investigator grants permission to authorized representatives of Galil and/or local regulatory authorities to conduct on-site monitoring visits for the purpose of reviewing the collected registry data and to review site procedures employed in the conduct of TRACE.

11. Adverse Events

All potentially related and directly related cryoablation adverse events (AEs), serious adverse events (SAEs) and unanticipated adverse device effects (UADEs) that occur within **30 days after the cryoablation procedure** is performed will be recorded. The cryoablation AEs, SAEs, and UADEs identified within the first 30 days after the cryoablation procedure will be followed and reported until resolution or for a period of 6 months.

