6.5.2 Adverse Events

Intra-operative device complications will be recorded, and whether or not the complication was related to the malfunction of the cryoablation system. Intra-operative patient complications will also be recorded.

All potentially related and directly related cryoablation adverse events (AEs), serious adverse events (SAEs) and unanticipated adverse device effects (UADEs) that occur within 30 days after the cryoablation procedure will be recorded.

The investigators will use the National Cancer Institute (NCI) Common Toxicity Criteria for Adverse Events [CTCAE] (version 3.0) grading system, and also the Clavien classification. AE terms will be selected from a pre-specified code list within the eCRF, and will be auto-coded within the eCRF using the CTCAE Short Term.

The incidence of AEs will be the number of patients who had the AE (counted only once) divided by the number of patients in the analysis population and represented as a percentage.

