8.3.2 Renal Cell Carcinoma (RCC) Population

The RCC population will be comprised of patients in the ITT population, with biopsy proven RCC and at least one lesion treated. Patients with biopsy proven RCC will be identified as patients having any of the following responses to either of the two questions “What is the frozen section pathology result?” and “What is the permanent section pathology result?

- Conventional, Renal Cell Carcinoma
- Papillary Renal Cell Carcinoma
- Chromophobe Renal Cell Carcinoma
- Collecting Duct Renal Cell Carcinoma
- Renal Cell Carcinoma, unclassified

Patients with a single lesion treated will be identified using the eCRF field “Number of lesions subjected to cryoablation” on the Procedure eCRF page.

This population will be used for the analysis of efficacy and AE data.

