8.7 Analysis of Safety

Safety analyses will be performed on both the ITT and RCC populations. The procedural and intra-operative data will be given for both the ITT and RCC populations.

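### The widest population used for safety omits treated patients later judged ineligible, so no summary adverse event rate covers everyone in whom cryoablation was attempted

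*SAP*

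**What the plan says.** SAP 8.3.1 describes the ITT population as patients with an attempted procedure on the sponsor's system and needles who met the eligibility criteria. It then gives the derivation:

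- Step 1: "First include all patients with a date of cryotherapy recorded".
- Step 2: "Then exclude any patients who have been manually identified as having not met all eligibility criteria from a review of monitoring reports".

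On its use, the section says: "This population will be used for the analysis of all efficacy and safety data".

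There is one other population. SAP 8.3.2 states: "The RCC population will be comprised of patients in the ITT population". SAP 8.7 adds: "Safety analyses will be performed on both the ITT and RCC populations". Under SAP 6.5.2, AE incidence is the number of patients with the event "divided by the number of patients in the analysis population and represented as a percentage".

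Protocol 8.3 sets a different rule: "All subjects completing a cryoablation procedure for removal of a renal lesion will be included in the analyses of TRACE data". It makes no exception for patients found ineligible, and it leaves the full analysis details to the SAP. SAP 5.2, which lists changes from the protocol's planned analyses, does not mention the eligibility exclusion.

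On how ineligibility comes to light, Protocol 10.1 has sites managed remotely by telephone, with on-site visits only when needed, and says "no routine monitoring visits will be conducted". SAP 8.2 keeps no record of protocol deviations.

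**The concern.** A patient who undergoes the procedure is exposed to its harms whether or not someone later decides that an entry criterion was missed. A safety set that drops such patients does not describe everyone exposed. Protocol 6.4 presents TRACE as a study of real-world outcomes, and use outside the entry criteria is part of real-world use.

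The exclusion is also made by hand, after treatment, from a source that is not systematic. The SAP names no reviewer, rule or cut-off date for the step. If sites were looked at with different intensity, two equally ineligible patients could be handled differently. The resulting set would then be neither all treated patients nor all eligible patients. This matters for AE tables by site (SAP 8.7.2) and for pooling sites on the premise of a common population (SAP 8.6.10).

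At stake are the AE, complication and procedural summaries, and to a lesser degree recurrence and survival, which use the same set.

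**Working it through.** **The populations side by side**

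| Source | Starting point | Eligibility exclusion | Used for |
|---|---|---|---|
| Protocol 8.3 | Procedure completed | None | All analyses |
| SAP 8.3.1 (ITT) | Procedure attempted; cryotherapy date recorded | Yes, by hand from monitoring reports | All efficacy and safety |
| SAP 8.3.2 (RCC) | ITT, biopsy-proven RCC, at least one lesion treated | Inherited from ITT | Efficacy, safety |

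RCC is a subset of ITT and safety uses only these two sets. A patient removed at step 2 is therefore absent from both the numerator and the denominator of every AE incidence and its interval. This follows from the text alone.

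**Size**

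The plan states no exclusion count, AE rate or power, so there is no figure of its own to reproduce. The planned size of about 250 comes from Protocol 8.1 and SAP 4.4. Everything else here is an assumption.

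Let n be the number excluded, with AE risk 10% in those kept and 20% in those excluded. The all-treated rate is [0.10 × (250 − n) + 0.20 × n] / 250.

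- n = 12: (23.8 + 2.4) / 250 = 26.2 / 250 = 10.5%. About 2 patients with an AE leave the tables.
- n = 25: (22.5 + 5.0) / 250 = 27.5 / 250 = 11.0%. About 5 patients with an AE leave the tables.
- The rate in the SAP's ITT set is 10.0% in both cases.

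Varying the assumptions, in whole patients with Wilson 95% intervals (the SAP's method for these percentages):

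| Excluded | AE risk in those kept | Risk in excluded | ITT set | All treated |
|---|---|---|---|---|
| 12 | 10% | same | 24/238 = 10.1% (6.9 to 14.6) | 25/250 = 10.0% (6.9 to 14.3) |
| 12 | 10% | 3 times | 24/238 = 10.1% (6.9 to 14.6) | 28/250 = 11.2% (7.9 to 15.7) |
| 25 | 20% | same | 45/225 = 20.0% (15.3 to 25.7) | 50/250 = 20.0% (15.5 to 25.4) |
| 25 | 20% | 3 times | 45/225 = 20.0% (15.3 to 25.7) | 60/250 = 24.0% (19.1 to 29.7) |

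**Rare events**

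For an event of incidence r, the chance that at least one excluded patient had it is 1 − (1 − r)^n.

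- n = 12: 11% for r = 1%, and 31% for r = 3%.
- n = 25: 22% for r = 1%, and 53% for r = 3%.

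**Uneven detection**

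Assume 10 sites of 25 patients with 5% ineligible, which is 12.5 patients in all. If ineligibility could come to light at only 2, 5 or 8 sites, then 2.5, 6.25 or 10 patients would be excluded. The other 10, 6.25 or 2.5, equally ineligible, would stay in.

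**The case against.** The case on the other side has five parts.

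- **The events are not lost.** AE recording and 24-hour reporting of serious events are unaffected (Protocol 11.2, 11.3). SAP 7.1 promises listings of all eCRF data and does not limit them to ITT. SAP 8.1 counts enrolment by population and by site. This stands: a reader might infer that these harms vanish from the report, and the documents do not support that. What is missing is any summary rate or interval for all treated patients, and any table of reasons for exclusion.
- **Dependence on site visits is not stated.** It is tempting to say that exclusion turns on which sites were visited. The SAP does not define monitoring reports, which could include telephone contacts. Entry criteria are recorded at baseline (SAP 6.3), and the sponsor's staff review all eCRFs (Protocol 9.2). Only the weaker statement is supported: detection probably varies with monitoring intensity.
- **The direction of bias is unknown.** A reader might infer that the exclusion must lower AE and recurrence rates. Baseline metastases or earlier therapy on the lesion could plausibly mean worse outcomes. Recent use of an investigational product, availability for follow-up and missing consent have no evident link to AE risk. The direction cannot be asserted.
- **The protocol contrast is not one-sided.** The SAP counts attempted procedures and the protocol counts completed ones, so the SAP is the wider of the two in a respect that matters for safety. The protocol also defers details to the SAP. The undeclared eligibility exclusion remains.
- **An eligible set is defensible for efficacy.** New metastatic disease cannot sensibly be assessed in a patient who had metastases at entry, and earlier therapy on the index lesion complicates recurrence. This stands, so the argument for all attempted procedures as the main set applies to safety only.

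**Conclusion.** The point holds for safety. As written, the SAP yields no summary AE incidence or confidence interval for all patients in whom cryoablation was attempted. It departs from Protocol 8.3 without saying so, and the selection probably rests on uneven detection. These conclusions come from the text, except that uneven detection is an inference from Protocol 10.1 and SAP 8.2.

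The size is unknown. Under the assumed 250 treated, 12 to 25 excluded and doubled risk in the excluded, the understatement is 0.5 to 1.0 percentage points, well inside the sampling uncertainty. It is 0.2 points or less at equal risk, and about 1 to 4 points in the tripled-risk cases shown. The chance of dropping a patient with an uncommon event may matter more than the shift in the overall rate.

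TRACE is a descriptive registry that SAP 4.4 says is not powered for formal analysis, and the exclusions may be few. The point should be fixed because the remedy is cheap, but nothing in the documents shows that the results are materially distorted or that exclusions were chosen by outcome.

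**What to change.** 1. Add a safety population to SAP 8.3: all consented patients in whom a procedure was attempted with the sponsor's system and needles, regardless of later eligibility findings. Use it for all AE, complication and procedural tables. Applying step 1 alone would not be enough, because a cryotherapy date by itself carries neither the device condition nor consent.
2. Keep the eligible set for efficacy, but rename it, since it is not an intention-to-treat set. Add a sensitivity analysis of recurrence and survival in all attempted procedures.
3. Tabulate exclusions from the eligible set by site and reason, and state what counts as a monitoring report and who makes the decision.
4. Declare the departure from Protocol 8.3 in SAP 5.2.

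The cost is SAP wording and some extra tables. AE rates may look slightly less favourable.

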8.3.2 Renal Cell Carcinoma (RCC) Population

The RCC population will be comprised of patients in the ITT population, with biopsy proven RCC and at least one lesion treated. Patients with biopsy proven RCC will be identified as patients having any of the following responses to either of the two questions “What is the frozen section pathology result?” and “What is the permanent section pathology result?

- Conventional, Renal Cell Carcinoma
- Papillary Renal Cell Carcinoma
- Chromophobe Renal Cell Carcinoma
- Collecting Duct Renal Cell Carcinoma
- Renal Cell Carcinoma, unclassified

Patients with a single lesion treated will be identified using the eCRF field “Number of lesions subjected to cryoablation” on the Procedure eCRF page.

This population will be used for the analysis of efficacy and AE data.

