6.2. Inclusion Criteria

Patients are required to meet all of the following criteria to be eligible for participation in the registry:

1. Patient is at least 18 years of age.
2. Patient has a renal lesion suspicious for malignancy.
3. Patient is to undergo renal lesion cryoablation via a Galil Medical cryoablation system using Galil Medical needles for treatment of primary or recurrent disease.
4. Patient is to be available for long-term follow-up per the enrolling physician's standard care practices.
5. Patient has provided written informed consent.

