7.1. Pre-Cryoablation Evaluation

Subjects will be enrolled in TRACE during their pre-cryoablation visit. The registry will collect data on the lesion characteristics, selected procedural parameters, associated safety measures, and short- and long-term clinical outcomes of the cryoablation procedure. The following information will be collected on all subjects entering the registry:

A. Data to be Collected by the Investigator and/or Study Coordinator

- Demographics (e.g., date of birth, gender, ethnicity)
- Height and weight
- ASA Classification
- Comorbidities (e.g., diabetes, hypertension, obesity, clotting disorder)
- Present Medical history
 - Incidental or symptomatic finding
 - Renal status
 - Previous renal surgery / History of suspicious lesion
- Cancer(s) other than renal
- Pertinent medication classes
- Smoking history
- Baseline Imaging
 - Type of imaging
 - Number of lesions identified (measures for each lesion should be recorded separately)
 - Lesion location: anterior, lateral, posterior, upper pole, mid-segment, lower pole, medial, hilar (within 5 mm of the renal hilum), with the following classification of the percentage of the mass that extends into the normal renal parenchymal border⁶
 - Exophytic- <40%
 - Mesophytic-40-60%
 - Endophytic- more than 60%
 - Lesion size measured by two methods:
 - 1) 3-dimensional measurements (cm) and
 - 2) Greatest trans-axial diameter (cm)
 - Lesion shape (spherical or non spherical)
 - Nephrometry Score
 - Hounsfield units
- Pre-Cryo Biopsy (if available)
 - Date
 - Type of biopsy (FNA or Core)
 - Number of cores taken
- Pre-Cryo Pathology (if available)
 - Classification of Lesion
 - Fuhrman Grade

- Clinical Laboratory Assessments (if available)
 - Creatinine
 - Estimated Glomerular Filtration Rate (eGFR)⁵
 - CBC (WBC, HCT, Hgb, Platelet)
 - BUN
 - LFT
 - PT
 - PTT

B. Baseline Quality of Life Questionnaire

Enrolled subjects will complete the Short Form-12 (SF-12) during the office visit. The SF-12 is a brief (twelve-item) health status survey to monitor outcomes in general and specific populations.

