8.4 Demographic and Other Baseline Characteristics

All demographic and baseline summaries will be displayed for the ITT and RCC populations.

Gender, race, ethnicity, will be summarized using counts and percentages. Age (at date of cryoprocedure, computed using the date of birth), height, weight and BMI will be summarized with descriptive statistics (number of patients [n], mean, standard deviation (SD), median, 25th percentile (p25), 75th percentile (p75) minimum (min), and maximum (max)). Age group (≥ 18 to < 65 years, ≥ 65 to < 75 years, and ≥ 75 years) will be summarized using counts and percentages.

The ASA physical status classification will be summarized using counts and percentages. The number and percentage of patients with medical history events will be summarized. Also, the number and percentage of patients with a history of smoking (current smoker, ex-smoker, never been a smoker) will be given.

Disease related baseline characteristics will be summarized using counts and percentages as follows:

- Previous renal surgery
- On dialysis
- Kidney affected
- Index lesion an incidental or symptomatic finding
- Recurrent disease
- Total number of lesions subjected to cryoablation
- Biopsy performed on the lesion to be treated during the cryoprocedure for the study (note: if multiple lesions were treated, each lesion may not have individual biopsy results)
- At least one malignant lesion by frozen section pathology; a response of “Malignant” in the eCRF field of “What is the frozen section pathology result?” will be classed as a “Yes” for this endpoint, and responses of “Benign”, “Not otherwise specified”, or “Not Done” will be classed as a “No”.
- At least one malignant lesion by permanent section pathology; a response of “Malignant” in the eCRF field of “What is the permanent section pathology result?” will be classed as a “Yes” for this endpoint, and responses of “Benign”, “Not otherwise specified”, or “Not Done” will be classed as a “No”.

Maximum lesion size, using the greatest trans-axial diameter, will be summarized with descriptive statistics and also as categories of ≤ 4 cm and > 4 cm. The maximum lesion volume will also be summarized.

The following lab parameters will be summarized with descriptive statistics:

- eGFR
- sCR; will also be summarized separately for patients with a history of hypertension, for patients with a history of diabetes, for patients with a

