history of both hypertension and diabetes; and by NS categories at baseline of low, moderate and high complexity (as defined in Section 6.3).

- Blood urea nitrogen (BUN)
- White blood cell (WBC)
- Hematocrit
- Hemoglobin
- Platelets
- Alanine aminotransferase (ALT)
- Aspartate aminotransferase (AST)
- Alkaline phosphatase (serum) (ALP)
- Alkaline phosphatase (plasma) (AKP)
- Total bilirubin (TBIL)
- International normalized ratio (INR)
- Prothrombin time (PT)
- Partial thromboplastin time (PTT)

CKD stages at baseline will be summarized with counts and percentages.

The total NS at baseline will be summarized with descriptive statistics, and also according to the categories of low, moderate and high complexity (as defined in Section 6.3). The individual R, E, N, A and L components of the NS will be summarized with counts and percentages. NS at baseline will also be summarized separately for patients with a history of hypertension, for patients with a history of diabetes, and for patients with a history of both hypertension and diabetes.

The following lesion characteristics will be summarized in a per-lesion summary (i.e., over the total number of lesions recorded in the study for descriptive statistics, and as a percentage of the total number of lesions for categorical data):

- Lesion size, by greatest trans-axial diameter, will be summarized with descriptive statistics and also as categories of ≤ 4 cm and > 4 cm
- Lesion volume will be summarized with descriptive statistics
- Duration (months) between date of baseline imaging and date of cryoprocedure will be summarized with descriptive statistics
- The type of imaging used (CT, MRI, ultrasound)
- Lesion location
- Lesion classification
- Lesion shape
- Cystic or solid lesion
- Hounsfield units, separately for each of following phases
 - Non-contrast
 - Arterial Phase
 - Venous Phase
 - Delayed Phase

- Area suspicious for lesion recurrence according to Hounsfield units (as defined in Section 6.3)
- The following biopsy related data will be summarized for all patients and separately by each site
 - Biopsy performed?
 - Duration (months) between date of biopsy sample and date of cryoprocedure will be summarized with descriptive statistics
 - Type of biopsy
 - If a core biopsy was performed, number of cores taken
 - Frozen section pathology result
 - Frozen section pathology classification
 - Permanent section pathology result
 - Permanent section pathology classification
 - Fuhrman classification grade

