8.8 Other Analyses

8.8.1 Post-treatment lesion characteristics

The analyses described in this section will be performed on the ITT and RCC populations.

The following lesion characteristics will be summarized in a per-patient summary, separately for each post treatment visit:

- Duration (months) between date of cryoprocedure and date of imaging will be summarized with descriptive statistics
- The type of imaging used (CT, MRI, ultrasound)
- Number of new lesions identified which were not present at baseline
 - Number of new lesions that are ipsilateral
 - Number of new lesions that are contralateral

The following lesion characteristics will be summarized in a per-lesion summary, separately for each post treatment visit (i.e., over the total number of lesions recorded in the study for descriptive statistics, and as a percentage of the total number of lesions for categorical data):

- Lesion in right or left kidney (right, left)
- Lesion size, by greatest trans-axial diameter, will be summarized with descriptive statistics and also as categories of ≤ 4 cm and > 4 cm
- Lesion volume will be summarized with descriptive statistics
- The type of imaging used (CT, MRI, ultrasound)
- Lesion location
- Lesion classification
- Lesion shape
- Cystic or solid lesion
- Hounsfield units, separately for each of following phases
 - Non-contrast
 - Arterial Phase
 - Venous Phase
 - Delayed Phase
- Area suspicious for lesion recurrence according to Hounsfield units (as defined in Section 6.4.1)
- Biopsy performed?
- Duration (months) between date of cryoprocedure and date of biopsy sample will be summarized with descriptive statistics
- Type of biopsy
- If a core biopsy was performed, number of cores taken
- Frozen section pathology result
- Frozen section pathology classification
- Permanent section pathology result
- Permanent section pathology classification
- Fuhrman classification grade

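### SAP 8.3.2 sets no cut-off date for the biopsy that proves RCC, so post-treatment pathology can decide membership of the RCC population; the field it names also conflicts with SAP 8.4

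*SAP*

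**What the plan says.** SAP 8.3.2 takes ITT patients with at least one treated lesion and biopsy-proven RCC. Proof is defined as follows: "Patients with biopsy proven RCC will be identified as patients having any of the following responses to either of the two questions". The questions are the frozen-section and permanent-section pathology results, and five RCC types qualify. No date, visit, lesion or eCRF page is attached to them. The same section does give a page for the number of lesions treated, which is read "on the Procedure eCRF page". On use, it states: "This population will be used for the analysis of efficacy and AE data". SAP 5.2 and 8.8.4 add renal function.

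Histology is not needed to enrol. Protocol 6.2 asks only that "Patient has a renal lesion suspicious for malignancy", and Protocol 7.1 and Table 1 collect pre-procedure and intra-operative pathology only where available. Pathology is also collected during follow-up (SAP 6.1). For each post-treatment visit, SAP 8.8.1 lists frozen and permanent section results and, separately, items such as "Permanent section pathology classification".

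SAP 8.4 uses the same two result questions at baseline. The item beginning "At least one malignant lesion by frozen section pathology; a response of" treats Malignant as yes, and Benign, Not otherwise specified or Not Done as no. Further down, 8.4 lists "Frozen section pathology classification" as its own item, apart from the result.

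**The concern.** A population analysed from the day of the procedure should be fixed by what was known by that day. Under 8.3.2 as written, a patient with no diagnostic specimen at treatment joins the RCC population if a later biopsy shows RCC. Protocol 8.4 makes biopsy one of the grounds for calling recurrence, so a later biopsy is plausibly linked to the outcome. A comparable patient whose follow-up raises no suspicion has less reason to be biopsied and would stay out. Time to recurrence, disease-specific survival and overall survival all run from the cryoprocedure (SAP 8.6.6), so a late entrant is also credited with follow-up from before the qualifying biopsy.

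At stake are the RCC estimates of recurrence and survival, the visit-by-visit recurrence percentages, and the RCC baseline, adverse event and renal function tables. The histological-type covariate in SAP 7.2 also states no time limit.

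The field mismatch makes matters worse. A programmer who finds no subtype in the result fields must substitute another field, and would then choose between baseline and all-visit records without instruction.

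**Working it through.** **No plan figure to reproduce.** The documents give about 250 patients, no power calculation, no recurrence rate and no RCC count. Every input below except 250 is an assumption.

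**Formula.** Let n0 be the patients proven at or before treatment, e0 their recurrences, k the late entrants, and q the share of late entrants with a counted time-to-recurrence event.

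Rate with late entrants = (e0 + q·k) / (n0 + k)

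This exceeds e0/n0 exactly when q > e0/n0. The direction therefore depends on q.

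**Central example.**
- Proven at treatment, 60%: n0 = 0.60 × 250 = 150. Recurrence 10%: e0 = 15.
- Unproven: 100. Half truly RCC: 50. Recurrences at 10%: 5. Half biopsied and positive: k = 2.5. All counted as events: q = 1.
- With a date limit: 15/150 = 10.0%. As written: (15 + 2.5)/152.5 = 11.5%.

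**Varying k and q** (n0 = 150, e0 = 15).

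| k | q | Rate |
|---|---|---|
| 2 | 1 | 17/152 = 11.2% |
| 5 | 1 | 20/155 = 12.9% |
| 10 | 1 | 25/160 = 15.6% |
| 5 | 0.5 | 17.5/155 = 11.3% |
| 5 | 0.10 | 15.5/155 = 10.0% (break-even) |
| 5 | 0 | 15/155 = 9.7% |

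For scale, the Wilson 95% interval is 6.2% to 15.8% for 15/150 and 8.5% to 19.1% for 20/155. A shift of this size lies within sampling error, but it is systematic and avoidable.

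**Grid** (q = 1; 50–70% proven at treatment, 5–15% recurrence, 30–70% of unproven lesions RCC, 25–75% of recurrences biopsied positive). Late entrants number about 0.3 to 9.8, and the rate ratio against the date-limited population is 1.03 to 1.49.

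**Kaplan-Meier check at 60 months** (simulation, 2,000 runs, 250 patients, 30% exponential loss by 60 months assumed, q = 1). Date-limited versus as written: 5.0% versus 5.2% in the mildest case, 10.0% versus 11.5% in the central case, and 10.0% versus 14.5% and 15.0% versus 21.3% in the strongest cases.

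**Field check.** SAP 8.3.2 expects answers such as papillary or chromophobe RCC to the result questions. SAP 8.4 gives those questions four answers, none of them a subtype. SAP 8.4 and 8.8.1 both list classification as a separate item. The sections do not agree on where the subtype is held.

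**The case against.** The strongest reply is that 8.3.2 is silent on timing and does not say that later biopsies count. The two questions appear in wording elsewhere only in 8.4, under baseline characteristics. Where the SAP means a follow-up field it usually says so: 6.4.2 to 6.4.4, 6.4.8 and 6.4.9 all name a follow-up page. A programmer could fairly read 8.3.2 as baseline pathology, and the eCRF that would settle it is not available. This stands as a reason not to claim that bias has occurred. It does not close the gap, because nothing in either document limits 8.3.2 to pathology obtained by the time of treatment.

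A reader might infer that late entrants are mostly treatment failures, so that RCC recurrence is certainly inflated. The documents do not support that. An event requires status Recurrent with contrast enhancement (SAP 6.4.4), progression does not count (5.2), and a recurrence after two or more missed visits is censored earlier (8.6.6.1). Positive biopsies from progressing lesions, non-enhancing recurrences or new lesions would add patients without events. Nor does SAP 6.4.3 confine follow-up biopsy to suspected recurrence.

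A reader might also infer that the rule, applied literally, selects nobody. That holds only if the answers listed in 8.4 are complete, and a rule that selects nobody could not also inflate recurrence. The defensible statement is that the sections conflict, and that whatever field is substituted still has no time limit.

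It is also true that ITT is used for all efficacy and safety data (8.3.1), that the study is not powered for formal analysis (4.4), and that neither document ranks RCC above ITT. These points limit the consequences.

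**Conclusion.** The concern holds as a defect in the definition. As written, membership of the RCC population can depend on a biopsy taken after treatment, while the clock starts at treatment. RCC recurrence is biased upward if late entrants have a counted event more often than patients proven at treatment; it is unbiased at equality and biased downward below that. For disease-specific survival the direction is uncertain: late entrants may have worse disease, but they had to survive to the biopsy.

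The size cannot be determined from the documents. The range of 1.03 to 1.49 in the rate ratio rests on assumed shares and on every late entrant having an event. The effect is small if few patients lacked pathology at treatment or few recurrences were biopsied. ITT is unaffected. The conflict between 8.3.2 and 8.4 over the subtype field is established from the text and must be reconciled whatever the number of late entrants.

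**What to change.** In SAP 8.3.2:
- Define RCC status from the frozen and permanent section classification fields on the pre-cryo or intra-operative pathology, name the eCRF pages, and require a specimen date on or before the index cryoprocedure.
- SAP 8.4 notes that lesions may lack individual biopsy results when several were treated. For those patients, use the patient-level pre- or intra-operative result.
- Keep patients first proven after treatment in ITT only, report their number, and give a sensitivity analysis that adds them to the RCC population.

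In SAP 7.2, apply the same time limit to histological type.

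The cost is a wording change, a date condition in the population flag and one sensitivity analysis. The dates should be available: 8.4 and 8.8.1 already derive intervals between biopsy and procedure, and 6.2.1.1 does not permit partial dates. The downside is a slightly smaller RCC population.
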